8.8 Stage 1 – Dose titration and tolerability (UK only)

The dose titration stage of the trial will involve two recruiting UK sites. The trial follows a design that titrates the dose of carbamazepine (CBZ) to a pre-specified optimum, based on clinical considerations. The trial aims for all Stage 1 participants to reach a dose of 20mg/kg by the end of the 12 month stage 1 period. Clinical judgement alongside clinical assessments will be used to determine a stable dose for the patient. Stable dose will be confirmed when a participant reaches a dose of 20mg/kg or the maximum dose at which they are able to tolerate any CBZ-related side effects (their maximum tolerated dose (MTD) and has a period of at least 8 weeks with no significant IMP related adverse events/side effects).

Stage 1 participants will be treated according to the dose titration regimen outlined below and detailed in Figure 2, following the guidance stated in the Guy's and St Thomas' NHS foundation Trust's paediatric formulary and British National Formulary (BNF) for Children for use of CBZ in children with epilepsy.

Figure 2 – Overview of design of dose titration & tolerability period from month 0 to 3

- Participants will be initiated on a daily CBZ dose of 5mg/kg/day. This daily dose will be divided, and participants will be asked to take CBZ twice daily. Doses may be taken during, after or between meals, with a little liquid e.g. a glass of water. If the current dose is tolerated by participants following 7 days of treatment, patients will be instructed to increase their daily dose by 5mg/kg/day for a further seven days
- The dose level will be increased every seven days until a maximum dose of 20mg/kg/day or MTD is achieved

8.8.1 Weekly dose evaluation call

At weekly intervals (+/- 1 day) following initiation of IMP treatment participants and or their parent(s)/legal guardian(s) will receive dose evaluation telephone calls from a medically qualified clinician from their local trial team to determine if the current dose has been tolerated, and to decide if the dose requires up-titration or other appropriate modification. Calls will be conducted by the site clinician or appropriately trained and delegated clinical staff. The participant will be contacted on a weekly basis until they reach a dose they can tolerate (either 20mg/kg or the nearest maximum tolerated dose). Additional calls can be conducted if the patient requires additional support. During the call the participant will be asked to provide information regarding drug side effects, adverse events, any changes to concomitant medication, drug compliance and details of any missed doses.

Participants will be provided with a Diary to record this information in between calls/visits. Medication counselling will be provided if required. All dosage decisions, IMP side effects, adverse events and any changes to concomitant medication noted during the dose evaluation calls should be documented in the patient notes by the appropriately trained and delegated member of the research team and in the appropriate eCRF within the trial MACRO database.

Dose titration decisions made during the trial dose evaluation telephone calls will be based on the occurrence of known CBZ side effects listed within the approved CBZ (Tegretol[®]) SmPC (Pl^b for Australia) and accompanying Patient Information Leaflet. If the participant does not report any side effects of significant concern, their dose will be up titrated by 5mg/kg to the next dose level up to a maximum dose of 20mg/kg.

If the participant is experiencing side effects/adverse events not of significant concern but in the clinical opinion of the investigator/clinician, is unlikely to tolerate a higher dose at the time of the weekly telephone call, then the dose should remain the same or lowered to the previous dose tolerated by the participant. At the discretion of the investigator/clinician, a further assessment call may be made the following week to consider continuing up-titration of CBZ by 5mg/kg increments, with weekly review as described above, unless this coincides with visit 1.2 where the assessment would take place during the visit.

If the participant is reporting any side effects /adverse events of significant concern to the clinician which are suspected to be related to the IMP as listed within the approved CBZ (Tegretol[®]) SmPC (PI^b for Australia) and/or accompanying Patient Information Leaflet, they will be asked to attend the trial site for laboratory safety blood assessments and further review. The results of the laboratory safety blood assessments, reported side effects/adverse events and clinical examination of the participant will be used to inform any changes to the participant's current dose.

If the participant is reporting any severe side effects as detailed in the CBZ (Tegretol[®]) SmPC (PI^b for Australia) and/or Patient Information Leaflet which prevent the participant from adhering to the trial protocol or in the opinion of the investigator deem the participant not suitable to continue participation in the trial then CBZ should be permanently discontinued and the patient withdrawn from the trial. The patient will be contacted again within 7 days to ensure the reasons for withdrawal have been resolved to the satisfaction of the investigator. If the participant experiences any severe side effects beyond the dose titration and tolerability stage, the same approach will apply.

Participants who do not tolerate increased dosing will be kept on a lower dose or the dose will be reduced. The inclusion of such patients in the final efficacy analysis will be discussed and evaluated case by case by the TMG with input from the IDMC if required (see section 8.8.4 – Missed doses).

If an adverse event is deemed to be serious, then a Serious Adverse Event form will also need to be completed (see protocol section 10.2 – Recording and reporting of AEs and SAEs) and sent to NCTU (UK only).

8.8.2 Dose evaluation safety visits – Week 2

To ensure patient safety during the escalation of dose from 5mg/kg to 20mg/kg participants and their parent(s)/legal guardian(s) will attend a site trial visit at week 2 (+/- 1 day). Blood samples will be taken to conduct the laboratory safety assessments described in section 8.7.5. Medication counselling will be provided if required. Once the outcomes of the laboratory safety assessments have been received at the trial site, a follow-up phone call will be made to the participant and their parent(s)/legal guardian(s) to discuss any requirement to alter their dose regimen. Additional assessments including

adverse event reporting and recording of concomitant medication will also be conducted during this visit as indicated in Table 6.

8.8.3 Dose evaluation safety visits – Months 3, 6, 9 & 12

Participants will be further assessed at clinic visits scheduled at 3, 6, 9 and 12 months post dose titration commencing. Assessments will include physical examination, Tanner stage, growth measurements, X-rays (left wrist for bone age and long leg standing AP), laboratory safety assessments, pregnancy testing (potentially child bearing females only), EQ-5D-Y questionnaire, PEDSQL questionnaires, AE recording, drug prescription & medication counselling, recording of concomitant medications and biomarker blood sampling (UK participants only) as detailed in the schedule of events Table 6.

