8.8.6 Dose finding review

An interim safety analysis will be conducted when at least six patients reach their MTD, which will allow modification of the regimen if required. The review will be led by the CI, Sponsor will be consulted and agreement from the trial IDMC will be sought. The review will be based on laboratory

safety assessments, adverse events and pain questionnaires. Treatment of the remaining stage 1 participants will not be delayed while this review is ongoing.

Once all 11 participants have reached 6 months (or those who are still continuing / not withdrawn), a safety review will be conducted to formally agree the IMP dose regimen to be implemented in Stage 2 of the study. Data to be reviewed includes laboratory safety assessments, adverse events, and pain questionnaires. The review will be led by the CI, Sponsor will be consulted and agreement from the trial IDMC will be sought.

Handling and review of data for both safety reviews will be performed in accordance with the trial Data Management Plan and Statistical Analysis Plan.

Participants who do not tolerate dosing will be kept on a lower dosing or dosing reduced. The inclusion of such patients in the final efficacy analysis will be discussed and evaluated case by case by the TMG with input from the IDMC if required.

Table 10 Timing and Frequency of reviews

Review	Time	Outcomes	IDMC agreement required
Interim safety analysis	First 6 patients reach MTD or 20mg/Kg	Primary outcome (SAFETY): Laboratory safety assessments, adverse events, pain scores and physical examinations collected post IMP administration.	Yes
Safety Review	11 th patient reaches the 6 month time point (or those who are still continuing / not withdrawn),	Primary outcome (DOSE) : Outcome of dose-titration safety review at 6 post IMP treatment initiation.	Yes, required to agree dose for Stage 2
Completion of Stage 1 safety analysis and Pain analysis	12 months from Baseline (when last patient recruited has reached 12 month time point) A further safety analysis will be presented to the IDMC on completion of Stage 1	 Primary outcome (SAFETY): Laboratory safety assessments, adverse events, pain scores and physical examinations collected post IMP administration. Secondary outcome (PAIN): Alteration from baseline in pain perception over 12 months as measured by: PEDSQL Pain Coping Inventory PEDSQL Pain Questionnaire 	No, to be presented at next IDMC meeting following analysis

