8.8.7 Continuation of treatment with CBZ for Stage 1 participants

Assuming Stage 1 participants have achieved their MTD and no significant safety concerns arise from the dose titration 6 month safety review, participants from Stage 1 will continue treatment with CBZ. They will receive the dose approved by the trial IDMC until they have received 24 months of IMP treatment (post initiation of IMP treatment) to allow their data to be included in the Stage 2 final analysis. If a participant has not reached the dose approved by the trial IDMC, they will continue on the maximum dose they were able to tolerate until they have received 24 months of IMP. Stage 1 participants will continue to attend trial visits every three months as indicated in the schedule of events –treatment (Table 7) and the participant visit schedule (Table 4). Eligible Stage 1 participants in the UK, who commenced treatment before 2nd March 2021, will have the option to continue treatment with CBZ for an additional 12 months after they have completed 24 months of IMP treatment. All trial visits must be completed by 31st January 2024.

Assuming the dose regimen is sufficiently similar in stage 1 and 2, stage 1 patients will be included in the analysis at the end of the trial, using the primary endpoint measured at the end of the dose titration phase for stage 1 and at the end of 12 months of treatment for stage 2. If the dose regimen changes between stage 1 and stage 2, we will consult with the IDMC as to whether stage 1 and stage 2 patients should be combined in the final analysis.

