11 STATISTICAL CONSIDERATIONS

11.1 Analysis Population

There will be two analysis populations:

- Patients who have completed the baseline observation period and have received at least one dose of CBZ
- Patients who have completed the baseline observation period and have received at least 75% of planned CBZ doses over the 12 -month treatment period

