4.2 Analysis populations

There will be two analysis populations:

1. Participants who have completed the baseline observation period and have received at least one dose of CBZ.

2. Participants who have completed their baseline observation period and have been prescribed, on average, at least 15 mg/kg of CBZ over their first 12 -months of treatment, i.e. a dose which is at least 75% of the dose recommended from Stage 1. Note that some participants will have longer than 12 months of treatment.

Adverse events will be reported for all participants who start their baseline period.

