4.3.2 Analysis

All patients who have completed the baseline observation period and have received at least one dose of CBZ will be included in the primary analysis.

Height measurements will be displayed graphically by individual indicating measurements taken during baseline and treatment periods.

Height measurement data will be analysed using the STATA commend **xtgee** to estimate the parameters of the regression model in 4.3.1. The parameter β_3 representing the change in growth velocity will be reported together with 95% confidence interval. The Huber/White/sandwich estimator of variance will be used to obtain confidence intervals [in STATA: vce(robust)].

If fitting the growth model in section 4.3.1 is problematic, for example, lack of convergence, then a simplified analysis will be considered.

For subject *i* (*i* = 1,..,*N*), let v_{ik} denote growth velocity (a continuous response variable) measured during the baseline period (*k*=1) and the treatment period (*k*=2). Growth velocity during the baseline period for each participant will be estimated using the first available and last available measurement during the baseline period; the growth velocity during the treatment period will be estimated in a similar manner.

The model for growth velocity is:

$$v_{ik} = \beta_1 + \beta_{2i} + \beta_3 P_k + \varepsilon_{ik},$$

where β_1 , β_{2i} and β_3 are regression parameters to be estimated using simple linear regression. P_k takes the value 0 for baseline period velocities (*k*=1) and 1 for treatment period velocities (*k*=2). As for the previous GEE model, the parameter β_3 represents the change in growth velocity between treatment and baseline periods. The parameter β_3 representing the change in growth velocity will be reported together with 95% confidence interval.

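### Protocol 8.8.1 and 8.8.6 leave it to the unblinded TMG to decide child by child whether children who did not tolerate dosing enter the efficacy analysis, against the fixed populations in Protocol 11.1 and SAP 4.3.2

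*Protocol*

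**What the plan says.** Two rules for the same children stand side by side.

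**Discretionary rule.** Protocol 8.8.1 deals with children kept on, or reduced to, a lower dose: "The inclusion of such patients in the final efficacy analysis will be discussed and evaluated case by case by the TMG". Section 8.8.6 repeats it, with inclusion "evaluated case by case by the TMG with input from the IDMC if required". Neither section gives a criterion, a deadline or any masking of the decision. Section 8.8.1 points to 8.8.4 (missed doses), which contains no rule on inclusion in an analysis.

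**Fixed rule.** Protocol 11.1 defines its first population as "Patients who have completed the baseline observation period and have received at least one dose of CBZ". Its second population is also a fixed rule, for those who "have received at least 75% of planned CBZ doses over the 12 -month treatment period". SAP 4.3.2 states: "All patients who have completed the baseline observation period and have received at least one dose of CBZ will be included in the primary analysis". Low dose is handled in SAP 4.2 and 4.3.4 by a sensitivity analysis restricted to children who "have been prescribed, on average, at least 15 mg/kg of CBZ over their first" 12 months.

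**Who decides, and what they can see.** There is no blinding (SAP 2.3). The TMG includes the CI, the statistician and co-investigators (Protocol 10.4.6), and Protocol 15.11 gives it access to the full dataset before publication.

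**Dates.** Protocol v9.0 is dated 16 October 2023 and contains both rules. The last visit could be no later than 31 January 2024. SAP version 1.0 is dated 8 February 2024. SAP 3.1.6 carries over the sentence about lower dosing without the TMG clause, and the SAP nowhere says that the clause is superseded.

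**The concern.** Tolerating the drug is itself a consequence of treatment. If some intolerant children are left out, the result no longer describes all treated children. If the choice is made with their heights in view, it can also follow the result. The trial has a single arm, so each child's change from baseline feeds directly into the estimate and no control group would show the effect of a selective exclusion. The primary objective is to judge whether efficacy warrants a development programme. A reader of the final report would need to know that the set of children behind that judgement was fixed by rule. With both rules in force, the documents do not establish this.

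**Working it through.** The documents state no SD, effect size or power (Protocol 11.3), so there is no figure of the plan's own to reproduce. The check has three parts.

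**1. Do the rules give different populations?** Take a child with a completed baseline who starts CBZ and is then held below 20 mg/kg. Protocol 11.1 (first population) and SAP 4.3.2 include the child. Under 8.8.1 and 8.8.6 the child may be in or out, as the TMG decides. The rules conflict for exactly the children the clause describes. Both clauses stand under 8.8, which is headed as Stage 1, so the literal reach is at most 11 of 11 + 29 = 40 children. Protocol 5.3 lets Stage 2 children be on a lower dose but has no TMG inclusion clause, so extending the clause to Stage 2 is an assumption.

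**2. Is the discretion needed to examine dose?** The SAP threshold is 0.75 × 20 = 15 mg/kg on average over the first 12 months. With the documented weekly 5 mg/kg steps, a child who never exceeds 15 mg/kg averages (7×5 + 7×10 + 351×15)/365 = 5370/365 = 14.71 mg/kg and falls outside the sensitivity set. A child who reaches and keeps 20 mg/kg averages (7×5 + 7×10 + 7×15 + 344×20)/365 = 7090/365 = 19.42 and is inside. The fixed rule already separates such children without any judgement.

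**3. How much could discretion move the result?** Assumptions, none from the documents except N = 40: true mean change in velocity 0; normally distributed within-child changes; m intolerant children, of whom all with a change at or below zero are dropped and the rest kept; a one-sample t interval.

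About m/2 children are dropped. The m/2 kept average +0.798 SD, the mean of the upper half of a normal distribution. So bias ≈ (m/2 × 0.798)/(40 − m/2), in SD units of the change:

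- m = 2: 0.798/39 = 0.02 SD
- m = 6: 2.394/37 = 0.065 SD
- m = 10: 3.990/35 = 0.11 SD

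Simulation agrees with these biases and gives the chance that the 95% CI lies wholly above zero:

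| m | Bias (SD) | CI wholly above 0 |
|---|---|---|
| 0 | 0 | 2.5% |
| 2 | 0.02 | about 3.3% |
| 4 | 0.04 | about 4.3% |
| 6 | 0.065 | about 5.8% |
| 10 | 0.11 | about 9.7% |

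Repeat runs differ by about 0.2 percentage points. If the SD were 1 to 2 cm/yr (an assumption), the biases for m = 2 and m = 6 would be 0.02 to 0.04 and 0.065 to 0.13 cm/yr.

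If all m children are dropped without regard to growth, the estimate shifts by (m/40) × d, where d is the tolerant minus intolerant difference in mean change. For d = 1 cm/yr and m = 2 to 6 that is 0.05 to 0.15 cm/yr. With d = 0 there is no bias and the upper tail stays at about 2.5%.

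**The case against.** The strongest reply is that the SAP already settles the matter. Protocol 11.2.1 leaves the full analysis to the SAP. The SAP is later than Protocol v9.0 and cites it, its primary set is unconditional, and 3.1.6 drops the TMG clause. SAP 2.1 also includes Stage 1 participants in the Stage 2 analysis. An analyst who follows SAP 4.3.2 has no discretion. This largely stands: the primary population could be chosen after the data were seen only if the team departed from both Protocol 11.1 and SAP 4.3.2. What remains is that the SAP omits the clause without withdrawing it. It did so after the latest permitted last visit in an open-label trial, and the protocol still contains both rules. The SAP's date is not itself a breach, since Protocol 11.2.1 asks only that it be agreed before the final analysis.

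Second, the clause sits in the Stage 1 section. This stands, and it limits the relevant range. Ten intolerant children would be 10 of 11 in Stage 1, which is hard to square with the IDMC agreeing 20 mg/kg with no changes (SAP 1.2). The m = 10 row is plausible only if Stage 2 is covered.

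Third, the simulation is a worst case. It drops every intolerant child with unfavourable growth and uses a t interval rather than the planned GEE with robust variance. This also stands.

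A reader might also take Protocol 8.8.7 as saying that children below the approved dose are included in the final analysis. It does not. The phrase about including data belongs to the sentence on children receiving the approved dose. The sentence on those below it says only that "they will continue on the maximum dose they were able to tolerate until they have received 24 months of IMP". It should not be cited as part of the contradiction.

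**Conclusion.** The inconsistency is real. Protocol 8.8.1 and 8.8.6 conflict with Protocol 11.1 and with SAP 4.3.2, and no text says which prevails. The clause permits exclusions by an unblinded group, after growth is known, without a criterion or deadline.

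A reader might infer that children were left out because of their results, or that the primary population is still open. The documents do not support either: they record no such exclusion, and the SAP's rule is unconditional. A reader might also treat the simulated percentages as error rates of the trial. They are not, because the documents set no success rule based on the confidence interval.

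On the literal Stage 1 reach, with 2 to 6 intolerant children assumed, the worst-case bias is about 0.02 to 0.065 SD, and the chance of an interval wholly above zero rises from 2.5% to between about 3.3% and 5.8%. About 0.11 SD and 9.7% would need 10 such children, and so reach into Stage 2. This should be fixed, and reconciled before the final analysis.

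**What to change.** - **Protocol 8.8.1 and 8.8.6:** delete the sentence on case-by-case inclusion in each and refer to 11.1. The text on dosing itself is untouched.
- **SAP 4.2:** add one line stating that every child with a completed baseline and at least one dose stays in population 1 whatever dose was tolerated, that no TMG or IDMC decision can remove a child from it, and that this replaces the inclusion sentences in Protocol 8.8.1 and 8.8.6.
- **Reporting:** present dose-restricted results only as the SAP 4.3.4 sensitivity analysis.

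The cost is two deleted sentences and one added line. The estimate may be slightly less favourable because children on lower doses stay in. The question of how efficacy looks at adequate dose is still answered by the sensitivity analysis.

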8.8.4 Missed doses

Participants will be provided with guidance regarding the management of their medication and what action to take if doses are missed in the form of the Diary. If a participant misses any doses, up titration decisions will require a participant to have demonstrated at least three consecutive days of 100% patient compliance immediately prior to up titration. If necessary, the treating clinician may instruct participants and their parent(s)/legal guardian(s) to remain at their current dose level for an appropriate amount of extra days before up titrating to the next dose level, if compliance is below this level to ensure compliance is met. Participants and their parent(s)/legal guardian(s) will be instructed to consult the research team for advice before up titrating under these circumstances if side effects/adverse events are experienced during the extra days. Any missed doses or variations in dose will be captured in the Diary and the eCRF.

